3 OBJECTIVES

3.1 PRIMARY OBJECTIVE:

To assess the feasibility and effectiveness of programs designed to detect and manage frail older patients in high risk clinical settings, and to avoid functional impairment and other associated adverse outcomes. These high risk settings will be medical wards (cardiology, oncology or nephrology), major surgery wards and Emergency rooms.

3.2 SECONDARY OBJECTIVES:

- Determine the feasibility of implementing clinical and therapeutic approach to geriatric physician in elderly patients in high risk clinical settings
- Determine disability by evaluating basic and instrumental activities of daily living in frail elderly patients treated in high risk clinical settings.
- Establish functional status in frail elderly people seen in high risk clinical settings.
- Evaluate quality of life through an instrument validated in frail patients seen in high risk clinical settings.
- Establish mortality ratio in frail patients included in high risk clinical settings.
- Obtain the rate of re-hospitalization in frail patients seen in high risk clinical settings.
- Determine the average stay of hospitalization in frail elderly patients treated in high risk clinical settings.
- Obtain the rate readmission to emergency room and hospitalization in frail older patients treated in high risk settings.
- Determine the average stay of hospitalization in frail elderly patients treated in high risk clinical settings.
- Determine the rate of delirium in frail elderly patients in high risk settings.
- Obtain the rate of health-care associated infections in frail older patients seen in high risk settings.
- Determine the rate of polypharmacy in frail older patients seen in high risk settings.
- Establish the secondary institutionalization rate accordingly to decline the functional status in frail elderly patients in high risk settings.

- Determine the need for a caregiver as a result of decline the functional status in frail older people in high risk settings.
- Establish the caregiver burden in hospitalized frail patients on high risk settings.
- Establish the secondary institutionalization rate accordingly to decline the functional status in frail elderly patients in high risk settings.
- Determine the need for a caregiver as a result of decline the functional status in frail older people in high risk settings.
- Establish caregiver burden of frail elderly patients seen in high risk settings.

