4 OUTCOMES

4.1 PRIMARY OUTCOMES:

1. **Disability:** It was measured by the Barthel Index for basic Activities of Daily Living and the Lawton index for instrumental activities of daily living.
2. **Functional status and performance-based measures:** Functional status and performance-based measures: Is measured by Short Physical Performance Battery (SPPB), Physical Activity Scale for the Elderly (PASE SCALE).
3. **Quality of Life:** Quality of life was assessed by self-reported questionnaire EuroQL 5D 5L. It will be measured during admission to hospital and follow-up.
4. **Geriatrician Intervention:** The impact of their intervention is measured by quantifying in a register any additional tests requested and medical advice by other specialists.

4.2 SECONDARY OUTCOMES:

Prevalence of Delirium: The delirium cases are detected by Confusion Assessment Method (CAM) scale.

Cognitive Impairment: Will be measured by the Mini Mental State Examination (MMSE) in the initial assessment.

Depression: will be assessed using the Geriatric Depression Scale in the baseline assessment.

Health-care associated infections: Acquired during hospitalization start.

Geriatric Syndromes: The geriatric evaluation including the following aspects: clinical, functional, mental and social.

Comorbidity: Will measured at initial assessment thorough Charlson index

Nutritional Status: Will measured at initial assessment thorough the Mini Nutritional Assessment and body Mass index.

Polypharmacy: Defined as five or more prescription drugs.

Mortality rate: Number of deaths during follow-up. It is calculated using official report of the National Statistics Institute (INE).

Average stay hospitalization: Average length of stay of stay all discharges. We will obtain from Hospital Admissions service.

Hospitalization Rate in Emergency room: Number of hospital admissions over the total of patients admitted in the hospital.

Readmission rates: Number of readmissions during of follow-up period. I will get the data in Hospital Admissions Service.

Institutionalization: Number of patients referred to nursing home after discharge or at any time during follow-up. This information is obtained directly from patients or their relatives.

Requirement of caregiver: Number of patients who require a caregiver after hospital discharge.

Caregiver burden: Will be used Zarit Scale for assessing caregiver burden

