5 STUDY DESIGN

This trial is designed as a randomised, multicenter, phase III trial to evaluate the feasibility and viability of clinical and therapeutic approach frail older people in high risk clinical settings (Emergency room, General Surgery, Oncology, Cardiology, and Nephrology). Patients will be randomized on a 1:1 basis to receive either usual treatment or usual treatment plus geriatric interventions.

The patients will be recruitment in Spain, Italy and United Kingdom. In Spain will be included the following centres: Hospital Universitario de Getafe (Madrid), Hospital Universitario Central de Asturias Monte Naranco (Asturias); In Italy: Ospedale San Raffaele (Rome), Universitat Cattolica del Sacro Cuore (Roma), in United Kingdom: (Cardiff University and other one to be determined) According to feasibility in each centre will be recruitment patients from differents clinical settings. See Table No 1

Table 1. Recruitment distribution of patients according to hospital and setting

Hospital	Setting
Hospital Universitario de Getafe. (Madrid - Spain)	Emergency room Cardiology ward Elective Surgery Emergency Surgery
Hospital Universitario Monte Naranco. (Asturias - Spain)	Oncology Elective Surgery Emergency Surgery
[name] (England – United Kingdom)	Emergency room Cardiology Ward Elective Surgery
Cardiff University (Wales - Reino Unido)	Emergency room Nephrology ward Elective Surgery
Ospedale San Raffaele (Rome - Italy)	Cardiology Ward
Universita' Cattolica del Sacro Cuore (Rome - Italy)	Emergency Room Cardiology Ward Elective Surgery

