9.3 EVALUATION AT 3 MONTHS OF DISCHARGE

Re-evaluate the following aspects by phone :

- Mortality
- Functionality data (Barthel index , Lawton index , PASE Scale).
- Usual medication.
- Residency at the moment.
- Frailty with the FRAIL scale..
- Data of quality of life with the scale EuroQolfive-dimensional (EQ-5D)
- Number of hospitalization and ER, indicate the cause (diagnosis)
- Caregiver burden with the economic questionaries .
- Economics evaluation, Index 3

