9.5 END OF THE STUDY EVALUATION

- The study will finish at 12 months after patient's discharge with a lastphone call .
- We should make an effort to write all the data during the study, at follow up and the final evaluation..

A follow-up and investigator's tasks schedule was performed during the study. See table 2.

Table 2 Schedule of the investigation

Intervention phase	Eligibility&recruitment	Initial Visit	Discharge	3 month Follow-up	12 month Follow-up
Informed consent	X				
Eligibility CI and CE	X	X			
Medical history		X			
Usual treatment		X	X	X	X
Comprehensive Geriatric Assessment		X			
Cognitive and depression (MMSE,GDS,CAM)		X			
Comorbidities - Charlson I.		X			
Functional Status (Barthel I, Lawton I, PASE, SPBB)		X SPBB	X Barthel	X	X
Sociodemographic data		X			
Physical Exam		X			
Nutritional Status (MNA)		X			
Permanent residence		X	X	X	X
Mean hospital stay			X		
Death			X	X	X
Frailty (Fried)		X	X		
Frailty(FRAIL)		X	X	X	X
EuroQolfive-dimensional (EQ-5D)		X	X	X	X
Caregiver burden		X	X	X	X
Relocation to other hospital services			X		
Adverse events (iatrogenic, falls, geriatric syndromes, etc.)		X	X		
Economics evaluation			X	X	X
Checklist of complementary test during the hospitalization			X		
Consultation to other specialist during hospitalization			X		

Coordination of care in different levels of care		X		
Readmission			X	X
Visits to the emergency room			X	X
Nosocomial infections		X		

* In case of surgical patients, who after 3 weeks since the first visit have passed and surgery hasn't been performed, evaluate the possibility of re-assessing inclusion criteria.

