Complementing the main cost-effectiveness analysis, we will develop several parallel cost effectiveness analysis to the extent that effective change. The results that we will use are: hospitalization rate and readmission, lenght of hospitalization and in the Emergency department, episodes of delirium and nosocomial infection, post-surgical complications as a whole and by surgical procedure, number of inappropriate drugs, adherence to treatment, permanent institutionalization rate, survival rate, preventable side effects due to under / over / mismanagement on caregiver burden.

Cost-utility analysis:

Cost-utility analysis (ACU) is an evolution of cost-effectiveness analysis, in which the interference effects are measured in a unit that synthesizes the lifespan and quality of life. The best and better known measure is the quality of life-adjusted per quality (QALY QALY or in its Anglo-Saxon sense). The QALYs are calculated by weighting the survival time (years of age) with quality adjustment thereof, called utility, which represents the preference values in relation to different health states (reference). For the purpose, the EQ-5D-5L instrument will be used. The incremental cost-utility relation answers the following expression:

$$\text{ACU}_{\text{incremental}} = (C_a - C_b) / (\text{AVAC}(a) - \text{AVAC}(b))$$

Statistical analysis:

A descriptive analysis of the main resources used in health care, social services and informal care will be performed.

This includes basic statistics such as means, medians, standard deviations, skewness, kurtosis, ranges, bivariate analysis using different cost elements and individual characteristics (sex, age,...) and health outcomes.

Because different distributions are expected from major cost components, we hope to develop different multivariate estimation methods. As we expect a non-normal distribution of the estimated costs, an alternative analysis would be the use of GLM models grouped by clusters, where depending on the distribution of the estimated costs (distribution Gamma, Poisson or Gaussian), will be used the most suitable method of empirical analysis. Another alternative, if the necessary information is obtained, could be an analysis using multilevel models of 2 or 3 grade (Recital country and center). The costs

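### The readmission outcome counts planned and unplanned admissions together, which pulls ratio measures towards 1 and adds noise; defining it as unplanned is a cheap improvement to a secondary outcome

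*Combined protocol and SAP*

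**What the plan says.** Section 4.2 defines the secondary outcome as "Readmission rates: Number of readmissions during of follow-up period" and names the source: "I will get the data in Hospital Admissions Service". It does not restrict the count to unplanned, emergency or related admissions.

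The follow-up calls in sections 9.3 and 9.4 ask for "Number of hospitalization and ER, indicate the cause (diagnosis"), that is, a number and a diagnosis. Table 2 lists readmission and emergency-room visits as separate items. Neither place records whether an admission was planned, and no analysis rule uses the cause.

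The settings in section 5 are "Emergency room, General Surgery, Oncology, Cardiology, and Nephrology". Table 1 splits surgery into elective and emergency; one hospital's entry, for example, reads "Oncology Elective Surgery Emergency Surgery". Elective surgery appears at five of the six hospitals, oncology at one and nephrology at one. The footnote to Table 2 shows that surgical patients may be enrolled with the operation still pending: "In case of surgical patients, who after 3 weeks since the first visit have passed and surgery hasn't been performed".

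The primary objective in section 3.1 is partly "to avoid functional impairment and other associated adverse outcomes". Section 10 uses readmission again as an effect measure in the parallel cost-effectiveness analyses: "The results that we will use are: hospitalization rate and readmission".

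**The concern.** A readmission that signals deterioration is the kind of adverse outcome the trial wants to avoid. A scheduled admission is not, yet the definition counts both alike. That some later admissions in oncology, nephrology and elective surgery will be scheduled is clinical judgement; the documents give no figure for it.

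Two different things can follow:

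- **Planned admissions about equal in both arms.** They add the same amount to each arm's rate. The ratio moves towards 1 by an amount that depends on the planned share. That share plausibly differs between settings, so one true benefit could show as different ratios across the settings that section 7.3 intends to combine in a meta-analysis.
- **Scheduled care changed by the geriatric plan.** The count can then move, in either direction, without any change in health. This is bias rather than dilution, and nothing in the documents allows it to be sized.

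The recorded diagnosis does not resolve the matter afterwards. The same cancer diagnosis can label a scheduled treatment stay or an emergency complication.

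**Working it through.** **The plan's own figure.** Section 7.3 sizes the trial on disability, not readmission. The smallest n with n × 0.4 − 1.96 × √(n × 0.4 × 0.6) ≥ 40 is 128. Multiplying by 1.2 gives 154, close to the stated 155 per arm per setting; dividing by 0.8 gives 160. The stated total of 1860 equals 6 × 310, whereas the five named settings give 5 × 310 = 1550. No figure is stated for readmission.

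**Inputs from the documents.** 155 per arm per setting, 1860 in total, 1:1 allocation, 20% drop-out, and 12 months of follow-up (sections 9.4 and 9.5). Evaluable per arm: 155 × 0.8 = 124 in one setting; 1860 × 0.8 / 2 = 744 in the whole trial.

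**Assumptions, not in the documents.** Unplanned readmissions of 0.8 per control patient-year; a 25% reduction, so 0.6 in the intervention arm; a planned rate P that is equal in both arms; one year at risk for everyone; deaths ignored.

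**Rate ratio and power.**
- Control mean m0 = 0.8 + P; intervention mean m1 = 0.6 + P.
- Ratio = m1 / m0; planned share in the control arm = P / m0.
- Var(log ratio) = (1/m0 + 1/m1)/n + 2k/n, with k = 0 (Poisson) or k = 0.5 (overdispersed).
- Two-sided 5% power = Φ(|log ratio| / SE − 1.96).

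Example, P = 0.2, n = 124, k = 0: ratio = 0.8/1.0 = 0.80; |log ratio| = 0.223; SE = √((1/1.0 + 1/0.8)/124) = 0.135; 0.2231/0.1347 = 1.66; power = Φ(1.66 − 1.96) = 38%.

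| P per year | Planned share | Rate ratio | Power, 124 per arm, k = 0 | Power, 744 per arm, k = 0 | Power, 744 per arm, k = 0.5 |
|---|---|---|---|---|---|
| 0 | 0% | 0.75 | 47% | 99.6% | 98% |
| 0.1 | 11% | 0.78 | 42% | 99% | 95% |
| 0.2 | 20% | 0.80 | 38% | 98% | 92% |
| 0.5 | 38% | 0.85 | 30% | 94% | 80% |
| 1 | 56% | 0.89 | 23% | 84% | 59% |

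**Difference in mean counts.** (0.6 + P) − (0.8 + P) = −0.2 for every P, so the planned admissions cancel. This is the form of the benefit term Ba − Bb in section 10. Only the noise grows: the Poisson SE is √((m0 + m1)/n), which for n = 744 is √(1.4/744) = 0.043 at P = 0 and √(3.4/744) = 0.068 at P = 1.

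**Any readmission, yes or no.** Section 7.4 names no rate ratio; it mentions prevalence and logistic models, among others. Assume unplanned readmission in 40% versus 30% of patients, and an independent chance q of a planned one. The observed proportions are then 1 − 0.6(1 − q) and 1 − 0.7(1 − q).
- q = 0.2: 52% versus 44%. The risk ratio moves from 0.75 to 0.85 and the risk difference from 10 to 8 points.
- q = 0.4: 64% versus 58%. The risk ratio is 0.91 and the risk difference 6 points.

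On this scale the absolute difference shrinks as well.

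**The case against.** All-cause readmission is a defensible outcome. Section 3.2 asks for the rate of re-hospitalization without qualification, and section 2.2 lists hospitalization as a poor outcome of frailty in the same unqualified way. It also needs no classification across three countries by staff who may know the arm. Part of the problem is already covered: cause is recorded, and emergency-room visits are a separate item. The outcome is one of many secondary ones, and the sample size does not rest on it. All of this stands, and it limits the point to a cheap improvement. It does not remove it, because a diagnosis does not show planned status and an emergency-room visit is not an admission.

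The documents do not support four stronger readings that a reader might infer:

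- **That a real reduction would be missed because of this definition.** In one setting, power under these assumptions is already only 47% with no planned admissions. In the whole trial it stays at 94% (Poisson) or 80% (overdispersed) with 0.5 planned admissions per year.
- **That planned admissions swamp the count.** Rates of 1 to 4 per year would make 56% to 83% of control readmissions planned (1/1.8 and 4/4.8). No passage supports such rates or says that treatment cycles are registered as admissions. Oncology and nephrology appear at one hospital each.
- **That results by setting cannot be compared.** Each randomized comparison within a setting remains valid. Ratios may differ with the planned share, which calls for care in reading them and no more.
- **That the cost-effectiveness ratio is diluted.** Equal planned counts cancel in Ba − Bb and add only noise.

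**Conclusion.** The definitional point holds: the rule mixes scheduled care with the adverse outcome of interest, and the planned data capture cannot separate them later. With planned admissions equal between arms, the direction follows by arithmetic: ratios move towards 1, and the difference in mean counts is unbiased but noisier. If the geriatric plan alters scheduled care, bias in either direction is possible; the equal-arms calculation does not cover that case.

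The size rests wholly on the assumed unplanned rate, effect and planned rates. Over planned rates of 0.1 to 1 per year the loss of power is small to moderate for the whole trial, and larger if counts are overdispersed. Within a single setting it worsens power that is already low. The whole-trial figures use the stated total of 1860 and a full year of follow-up; section 7.2 instead names month six as the last contact, and shorter follow-up would lower power at every planned rate. The primary outcomes are unaffected.

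**What to change.** - In section 4.2, define the readmission outcome for effectiveness as unplanned (emergency) hospital admissions after discharge.
- Classify each admission by the administrative admission type in the hospital record. Add a planned/unplanned field beside the cause already asked at the 3- and 12-month calls. That the hospital admission records carry this type at every site is an assumption to confirm.
- Use the same definition for the readmission-based cost-effectiveness analysis in section 10.
- Keep all-cause readmissions for costing and report them alongside the unplanned count. A difference between arms in planned admissions would then be visible.

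The cost is one line of definition and one data field. The field should be in place before follow-up starts, because later reclassification from diagnosis would be partial. The downside is that some admissions must be classified across three countries, possibly by staff who know the arm; relying on the administrative type limits that judgement.

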5 STUDY DESIGN

This trial is designed as a randomised, multicenter, phase III trial to evaluate the feasibility and viability of clinical and therapeutic approach frail older people in high risk clinical settings (Emergency room, General Surgery, Oncology, Cardiology, and Nephrology). Patients will be randomized on a 1:1 basis to receive either usual treatment or usual treatment plus geriatric interventions.

The patients will be recruitment in Spain, Italy and United Kingdom. In Spain will be included the following centres: Hospital Universitario de Getafe (Madrid), Hospital Universitario Central de Asturias Monte Naranco (Asturias); In Italy: Ospedale San Raffaele (Rome), Universitat Cattolica del Sacro Cuore (Roma), in United Kingdom: (Cardiff University and other one to be determined) According to feasibility in each centre will be recruitment patients from differents clinical settings. See Table No 1

Table 1. Recruitment distribution of patients according to hospital and setting

Hospital	Setting
Hospital Universitario de Getafe. (Madrid - Spain)	Emergency room Cardiology ward Elective Surgery Emergency Surgery
Hospital Universitario Monte Naranco. (Asturias - Spain)	Oncology Elective Surgery Emergency Surgery
[name] (England – United Kingdom)	Emergency room Cardiology Ward Elective Surgery
Cardiff University (Wales - Reino Unido)	Emergency room Nephrology ward Elective Surgery
Ospedale San Raffaele (Rome - Italy)	Cardiology Ward
Universita' Cattolica del Sacro Cuore (Rome - Italy)	Emergency Room Cardiology Ward Elective Surgery

6 ELEGIBILITY

6.1 INCLUSION CRITERIA:

Participants must meet all of the following inclusion criteria to be eligible to register for this trial: older than 75 years old diagnosed of frailty, according to Fried's Criteria, if is not possible to use the Fried Scale, FRAIL Scale will be used.

6.2 EXCLUSION CRITERIA:

- Do not able to give informed consent.
- Participants with moderate-severe cognitive impairment according to MMSE scale (score 18 or lower) and/or the GDS scale (score 5 or higher)*.
- Those with physical disability according to Barthel Index (lower to 40)
- Participants with critical acute disease who might need admission in an Intensive Care Unit (ICU).
- Life expectancy lower than six months
- Nursing home residents

* This cut-off was selected to establish a higher sensitivity and maintain a good recruitment rate.(24)

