2 INTRODUCTION

2.1 BACKGROUND INFORMATION:

Disability is the main consequence of the concurrence of three conditions in old people: the ageing process, lifestyle processes and health-related conditions.

As it has been the case with other relevant organizations and bodies, in its 2012 Ageing report, the European Commission and the Economic Policy Committee stated that coping with the challenge posed by an ageing population and a trend toward increases in age-related spending will require determined policy action in Europe, particularly in: (a) reforming pension, health care and long-term care systems, and (b) the reduction of disability and dependence through appropriate action with a special focus in fighting against disability (DG ECFIN & AWG, 2012).

Disability is usually preceded by a state characterized by a decreasing capacity to respond to demands, caused by diminishing functional reserve. This condition has been named frailty, a disorder that may precede by several years the development of disability (1) and other clinical outcomes. When the frailty threshold has been surpassed and disability has emerged, recovery from disability is unlikely (2), especially as the age of the patient, the degree of disability or its duration increase (3). In contrast, frailty is reversible, as it has been shown both spontaneously (4, 5) and by interventions based on physical exercise (6).

Moreover, and differently from chronic disease, the predictive capacity of frailty for adverse outcomes increases as the age of the population increases (8) becoming the most common condition leading to death among community-dwelling older persons, followed by organ failure (21.4%), cancer (19.3%) and dementia (13.8%) of dying.

The aim of the present study is to assess the feasibility and effectiveness of programs designed to detect and manage frail older patients in high risk clinical settings, and to avoid functional impairment and other associated adverse outcomes.

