7.3 SAMPLE SIZE

Dependence and disability affects quality of life perception and increases health costs. Hence, this variable will be taken to calculate sample size. According to literature, the incidence of disability in frail older people is approximately 40%.

In order to avoid the estimation bias, the sample size will have at least 10 outcomes as variables. Therefore, the formula has been calculated for a 95% confidence interval to obtain at least 40 events.

$$n * p \pm z_{1-\frac{\alpha}{2}} \sqrt{n * p * (1-p)}$$

It has been assumed drop-out rate of 20% and an incidence of disability described above. Hence, the sample size should be at least 1860 participants. In each clinical setting (emergency room, general surgery, oncology, cardiology and nephrology) 310 participants should be evaluated (155 in each group: control and intervention).

In case of not obtaining the minimal sample size in each clinical setting, the pondeate models will be made. Additionally, a meta-analysis will be performed including the global effect of the intervention according to clinical setting and with a thorough sensitivity analysis.

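### The trial is sized on incidence of disability in all patients but analysed as a prevalence without the entry score, although patients with some dependence may enrol

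*Combined protocol and SAP*

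**What the plan says.** - **Entry (section 6.2).** The only exclusion based on daily activities is "Those with physical disability according to Barthel Index (lower to 40". The Barthel form in the appendix totals 0 to 100, so scores from 40 to 100 are admitted. No limit is set on the Lawton index.
- **Outcome (section 4.1).** Disability is the first primary outcome. "It was measured by the Barthel Index for basic Activities of Daily Living", with the Lawton index for instrumental activities. The section gives no cut-off, no amount of change, no time point and no set of patients at risk.
- **Sizing (section 7.3).** Dependence and disability drive the calculation: "Hence, this variable will be taken to calculate sample size". The planning rate is given as "According to literature, the incidence of disability in frail older people is approximately 40" per cent, and "the formula has been calculated for a 95% confidence interval to obtain at least 40 events". No allowance is made for disability already present at entry.
- **Analysis (section 7.4).** The effect on each event is to be described first as a prevalence rate, and then by duration where that can be assessed. A Mann-Whitney test is named for differences between arms. The visit-0 score does not enter any of the comparisons described.
- **Background (section 2.1).** "When the frailty threshold has been surpassed and disability has emerged, recovery from disability is unlikely".

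**The concern.** An incidence counts new cases among people who do not yet have the condition. A prevalence counts everyone who has it at the time of assessment, whenever it began. The plan uses the first to choose the sample size and the second to estimate the effect, in a population where some patients may already be dependent. A patient with Barthel 45 and Lawton 0 is eligible, for example.

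If such patients are counted as cases at follow-up, disability that was there before randomisation appears as an outcome in both arms and pulls the two rates together. If only new disability counts, fewer patients are at risk than section 7.3 assumes. In either case a primary outcome is affected. Because the event is undefined, the choice between these readings could also be made after the data are seen.

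**Working it through.** **Inputs.** From section 7.3: incidence p = 0.40, at least 40 events, 95% interval, 20% drop-out, 155 per arm and 310 per setting. From section 6.2: Barthel 40–100 admitted. The share d already disabled at entry is not in the documents, so it is varied here as an assumption.

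**Reproducing the plan's figure.** Take the smallest n whose lower limit, n·p − 1.96·√(n·p·(1 − p)), reaches 40.
- n = 128: 51.2 − 1.96 × √30.72 = 40.3.
- Multiplying by 1.20 for drop-out gives 128 × 1.20 = 153.6, or 154, against the stated 155.
- Dividing by 0.80 gives 160, which is further from the stated figure.

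So 155 reproduces closely as a number per arm per setting, with all evaluable patients at risk of the 40% event.

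**Evaluable patients.** 155 × 0.80 = 124 per arm per setting. Expected events with everyone at risk: 124 × 0.40 = 49.6.

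**Reading A: only new disability counts.** Expected events = 49.6 × (1 − d).

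**Reading B: disability at follow-up is counted whenever it began, with no recovery.** Expected events = 124 × [d + 0.40 × (1 − d)]. If the rates of new disability in the two arms are a and b, the observed difference is [d + (1 − d)a] − [d + (1 − d)b] = (1 − d)(a − b).

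The last two columns take 40% v 30% among those at risk. This is only an illustration, because the documents state no treatment effect.

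| d | Events, A | Events, B | Observed rates, B | Risk ratio, B |
|---|---|---|---|---|
| 0% | 49.6 | 49.6 | 40% v 30% | 0.75 |
| 10% | 44.6 | 57.0 | 46% v 37% | 0.80 |
| 20% | 39.7 | 64.5 | 52% v 44% | 0.85 |
| 30% | 34.7 | 71.9 | 58% v 51% | 0.88 |

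Under A, the expected count falls below 40 once d exceeds 1 − 40/49.6, about 19%.

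Under B, the count rises but the contrast shrinks. With n = 7.849 × [p₁(1 − p₁) + p₂(1 − p₂)]/(p₁ − p₂)² per arm for 80% power at two-sided 5%:
- d = 0: 7.849 × (0.24 + 0.21)/0.10² ≈ 353.
- d = 30%: 7.849 × (0.2436 + 0.2499)/0.07² ≈ 790.

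**Reading C: disability means Barthel below 40.** The exclusion wording allows this. Then d = 0 by construction and everyone is at risk. The 40% would have to be the rate of falling below 40, which the documents do not state.

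**The case against.** A reader might infer that already disabled patients are enrolled who can never contribute an event, and that the 40-event target is therefore missed. The documents do not support that.

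- The only operational wording for disability is the exclusion itself. Read as a definition, it leaves nobody disabled at entry. If the event is a further decline from the entry score, every patient is again at risk.
- Section 7.3 takes the 40% from unspecified literature. Its threshold, population and time horizon are not stated, so neither a match nor a mismatch with the enrolled patients can be shown.
- The shortfall arises only under reading A with the floor applied per arm. At d = 20% it is 39.7 against 40. If both arms of a setting are pooled, 248 × 0.40 = 99.2 events are expected, and the count stays above 40 until d is about 60%. Section 7.3 links the floor to estimation bias and the number of variables, not to power.
- A reader might also infer that baseline disability forms a fixed block that treatment cannot alter. Section 2.1 calls recovery unlikely, not impossible, and section 8.2 aims to improve independence. A follow-up prevalence could therefore capture some recovery.
- Section 10 measures health benefit as change from baseline, so the idea is not absent from the document.

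These points stand, and they rule out a firm claim of too few events. They do not reconcile sections 7.3 and 7.4. Section 10 governs the economic evaluation only, and no section says how the entry score enters the comparison of disability between arms.

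**Conclusion.** The point holds as a mismatch between entry rule, sizing and analysis. Section 7.3 plans on incidence in all evaluable patients. Section 7.4 estimates a prevalence without the entry score. Section 4.1 defines neither the event nor who is at risk of it. As written, the analysis would mix disability present at entry with new disability on a primary outcome.

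The direction of the harm depends on the reading: dilution of the risk difference by (1 − d) if prevalent cases are counted, or a loss of events by the same factor if only new cases count. The size cannot be fixed from the documents, because d is not given. The figures above assume 124 evaluable patients per arm in a setting, a 40% incidence among those free of disability at entry, equal d in both arms and, for the prevalence reading, no recovery.

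**What to change.** This point asks for no change to the entry criterion.

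- **Sections 4.1 and 7.4.** Make the comparison of disability between arms a baseline-adjusted one: follow-up Barthel with visit-0 Barthel as covariate, and likewise for Lawton. Name the time point. Report incident disability separately, only in patients without it at entry, with the cut-off on each scale fixed before the data are seen.
- **Section 7.3.** State which event, population and horizon the 40% describes, after checking its source. Reconcile it with the prevalence rate in 7.4, and restate the expected events over a stated range of d.

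No extra data collection is needed. Sections 9.1 to 9.4 already collect Barthel at visit 0, discharge, 3 months and 12 months. Lawton is collected at visit 0, 3 months and 12 months but is not listed at discharge, so its adjusted comparison is available at the two later visits. The cost is new wording in three sections. The downside is that the stated event count may become less favourable.
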